7.3. Method of Study Treatment Assignment

Participants will be stratified as outlined in Section 5.1 and randomized 1:1 to receive daprodustat or darbepoetin alfa.

A randomization number will be assigned in accordance with the randomization schedule prepared in advance of the study by Clinical Statistics, GlaxoSmithKline, using validated internal software (Registration and Medication Ordering System Next Generation (RAMOS-NG)).

7.4. Blinding

This is an open-label study. However, a central FBF reader, who will read and evaluate the FBF data, will be blinded to the treatment assignment. Details of the blinding procedures can be found in the SRM.

7.5. Preparation/Handling/Storage/Accountability

- Daprodustat is to be stored at up to 30°C (86°F). Maintenance of a temperature log (manual or automated) is required.
- Darbepoetin alfa, acetylcholine, sodium nitroprusside and L-NMMA are to be handled and stored as per package labeling.
- The investigator, institution, or the head of the medical institution (where applicable) is responsible for study treatment accountability, reconciliation, and record maintenance (i.e., receipt, reconciliation, and final disposition records).
- Further guidance and information for the final disposition of unused study treatment are provided in the SRM.
 - Only participants enrolled in the study are to be administered any study treatments.

- Under normal conditions of handling and administration, study treatment is not expected to pose significant safety risks to site staff.
- A Material Safety Data Sheet (MSDS)/equivalent document describing occupational hazards and recommended handling precautions either will be provided to the investigator, where this is required by local laws, or is available upon request from GSK.
- The investigator or designee must confirm appropriate temperature conditions have been maintained during transit for all study treatment received and any discrepancies are to be reported and resolved before use of the study treatment.

7.6. Treatment Compliance

Participants that are randomized to daprodustat will be instructed to return all unused study treatment at each clinic visit. A record of the number of daprodustat tablets dispensed to and returned by each participant will be maintained and reconciled with study treatment and compliance records.

Participants that are randomized to darbepoetin alfa will have supervised administration of study treatment in the clinic, with the details of each administered darbepoetin alfa dose maintained and reconciled with study treatment and compliance records.

Study treatment start and stop dates and dosing details, including dates for study treatment dose increases or reductions, will be recorded in the electronic Case Report Form (eCRF).

7.7. Concomitant Therapy

Concomitant medications, including over-the-counter medications and supplements, taken during the study will be recorded in the eCRF. Start/stop dates and route of administration will be recorded for general concomitant medications. Additional details (e.g., changes in dose, reason for change, reason for addition or termination) will be recorded for certain medications at each visit (e.g., iron and anti-hypertensive medications).

NOTE: Participants should be maintained on the current dose and frequency of anti-hypertensive therapy, whenever possible.

7.7.1. Permitted Medications and Non-Drug Therapies

Unless specified as a prohibited medication in Section 7.7.2, all concomitant medications should be considered permitted provided they are not contraindicated for the individual participant concerned.

Participants are to be advised to maintain any anti-hypertensive medications at a consistent dosage and frequency; however, participants **are to delay administration of any anti-hypertensive medications until after all study-related procedures are completed on Days 1 & 42.**

Participants may take non-steroid anti-inflammatory drugs (NSAIDs) and aspirin during the treatment period; however, participants **are to avoid NSAIDs and aspirin for 24 hours prior to the FBF & PWV procedures until after all study-related procedures are completed on Days 1 & 42.**

7.7.2. Prohibited Medications and Non-Drug Therapies

No rhEPO use is permitted within the 12 weeks prior to the screening visit through Day 1.

Use of any of the following prohibited drugs from 1 week prior to screening until all assessments on Day 42 have been successfully completed is prohibited and will constitute a protocol violation, with the exception of strong cytochrome P₄₅₀ 2C8 (CYP2C8) inhibitors or inducers, which can be used for up to 14 days.

- Strong inhibitors of CYP2C8 (e.g., gemfibrozil, high dose clopidogrel [300 mg])
- Strong inducers of CYP2C8 (e.g., rifampin/rifampicin)
- Intravenous administration of iron
- Any rhEPO other than darbepoetin alfa administered as study treatment as per protocol

7.7.3. Standard of Care

During the study, investigators are expected to monitor the participant's overall clinical status to ensure standards of care are met to enable consistency of practice with Kidney Disease: Improving Global Outcomes (KDIGO) guidelines or local equivalent.

7.7.4. Iron Management Criteria

Participants must be iron replete, as per local/regional guidelines prior to randomization and must remain iron replete throughout the study. Oral iron is allowed during the course of the study.

Participants that receive IV iron during the treatment period (i.e., from Day 1 through Day 42) are to discontinue study treatment (See Section 8.1) and be withdrawn (See Section 8.2).

7.8. Treatment after the End of the Study

Participants will not receive any additional treatment from GSK after completion of the study. The investigator is responsible for ensuring that consideration has been given to post-study care of the participant's medical condition.

8. DISCONTINUATION CRITERIA

8.1. Discontinuation of Study Treatment

Participants that discontinue study treatment will be withdrawn from the study. See Section 8.2 for a description of withdrawal procedures.

A participant must discontinue study treatment for the pre-specified reasons below.

- Meets Hgb stopping criteria (See Section 8.1.2)
- Receives a blood transfusion
- Receives an AV fistula or graft
- Receives a kidney transplant
- Participant initiating dialysis
- Receives IV iron
- Becomes pregnant or intends to become pregnant during the study
- Diagnosis of cancer (new or recurrent), with the exception of localized squamous cell or basal cell carcinoma of the skin
- Need for more than 14 days use of a strong CYP2C8 inhibitor or inducer (See Section 7.7.2)
- Any other condition which in the opinion of the PI makes the participant unsuitable to continue in the study.

[figure not shown]
8.1.1. Liver Chemistry Stopping Criteria

Liver chemistry stopping and increased monitoring criteria have been designed to assure participant safety and evaluate liver event etiology.

Discontinuation of study treatment for abnormal liver tests is required when:

- a participant meets one of the conditions outlined in [Figure 3](#)
- OR**
- when in the presence of abnormal liver chemistries not meeting protocol-specified stopping rules, the investigator believes study treatment discontinuation is in the best interest of the participant.

Figure 3 Phase II Liver Chemistry Stopping and Increased Monitoring Algorithm

Liver Safety Required Actions and Follow up Assessments Section can be found in [Appendix 6](#).

8.1.2. Hgb Stopping Criteria

GSK will supply a point-of-care Hgb analyzer (HemoCue) to each site for rapid and convenient monitoring of Hgb levels and to ensure consistency of Hgb measurements across sites participating in the study.

Blood samples for measurement of Hgb concentrations via HemoCue will be collected and recorded in the eCRF. [Table 2](#) summarizes the Hgb values and corresponding action to be taken at each visit.

Table 2 Hgb Stopping Criteria

Hgb (g/dL) at visit		Action
<7.5		Repeat HemoCue assessment on the same sample at same study visit to confirm; take average of 2 values. If confirmed, permanently discontinue study treatment and withdraw participant from the study.
≥7.5 - <13.0 with:	≥2.0 g/dL decrease in Hgb over the previous 2 weeks	Repeat HemoCue assessment on the same sample at same study visit to confirm; take average of 2 values. If confirmed, permanently discontinue study treatment and withdraw participant from the study.
≥7.5 - <13.0 with:	≥1.3 g/dL increase in Hgb over the previous 2 weeks (at Day 15 only) ¹	Repeat HemoCue assessment on the same sample at same study visit to confirm; take average of 2 values. If confirmed, permanently discontinue study treatment and withdraw participant from the study.
≥13.0		Repeat HemoCue assessment on the same sample at same study visit to confirm; take average of 2 values. If confirmed, permanently discontinue study treatment and withdraw participant from the study.

¹ If increase in Hgb >1.3 g/dL is noted on Day 28, refer to Dose Modification (Section 7.2).

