¹⁰The initial dose of study treatment will be given **after** the completed Day 1/Repeat Day 1 FBF & PWV procedures. Participants will receive **EITHER** daprodustat **OR** darbepoetin alfa. The final dose of daprodustat will be Day 41 (i.e., the day prior to the FBF & PWV procedures), while the final dose of darbepoetin alfa will be Day 28. If repeat procedures are needed the dosing will be extended (See Section 9.6.1.4).

¹¹See Section 7.2 for details on study treatment adjustment

¹²Applies only to participants on anti-coagulant therapy; further details concerning measurement of the international normalised ratio (INR) and subsequent actions can be found in the study reference manual (SRM).

¹³If test otherwise performed within 3 months prior to first dose of study treatment, testing at screening is not required

¹⁴The FBF & PWV assessments are to be performed following confirmation of INR < 3.0 for participants on anticoagulant therapy. The Day 42 FBF & PWV assessments can be delayed up to 1 week (i.e., Day 49), while randomization (Day 1) should be delayed until the participant's INR < 3.0 (Section 9.6.1.1).

¹⁵Only serious adverse events (SAEs) assessed as related to study participation are collected at this visit. See Appendix 4 for additional details.

¹⁶As described in Section 9.8

¹⁷Indicates the procedures to be performed on the repeat visits only if the visit is deemed necessary. See Section 9.6.1.4

¹⁸Darbepoetin is only to be given on Day 42 if a Repeat Day 42 is needed.

- The timing and number of planned study assessments, including: safety, pharmacodynamic or other assessments may be altered during the course of the study based on newly available data (e.g., to obtain data closer to the time of peak plasma concentrations) to ensure appropriate monitoring.
- Any changes in the timing or addition of time points for any planned study assessments must be documented and approved by the relevant study team member and then archived in the sponsor and site study files, but will not constitute a protocol amendment. The IRB/IEC will be informed of any safety issues that require alteration of the safety monitoring scheme or amendment of the ICF.

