9.6.1.1. Participants on Anti-coagulant Therapy

In order to minimize blood loss from the FBF procedure, participants on anti-coagulant therapy are to have INR assessed prior to initiation of the procedure. Only participants with INR < 3.0 are to undergo the FBF & PWV assessments. Participants with INR \geq 3.0 can delay the Day 42 assessment up to 1 week (i.e., Day 49) in order to allow INR to decrease below 3.0 (See SRM for further details). For participants that will have delayed FBF procedures performed, details can be found in Section 9.6.1.4.

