9.6.1.3. FBF Quality Control Criteria

After both the Day 1 and Day 42 FBF procedures, the results will be checked for data quality as defined in the Study Reference Manual (SRM). If the FBF fails the quality control (QC) criteria following the Day 42 procedure, one additional attempt may be made in a subsequent visit up to 1 week later, if the participant agrees. For participants that will have repeat FBF procedures performed, details can be found in Section 9.6.1.4.

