9.6.1.4. Delayed or Repeat FBF Procedures

Delayed FBF Procedures: In the instance that the FBF procedure needs to be delayed, participants should either continue receiving the daprodustat dispensed on Day 28, while the participants randomized to darbepoetin alfa should receive an appropriate dose on Day 42. The assessments that are scheduled to be conducted on Day 42 are to be followed (See Section 2).

Repeat FBF Procedures: If the FBF procedure is determined to be repeated for either Day 1 or Day 42, the assessments should be performed as per the SoA Table at the additional FBF visit. The PWV procedures should also be repeated.

In the instance that the Day 1 FBF procedure needs to be repeated, the participant should not be dosed with study drug until after the repeat/completed procedure. The timing of all subsequent visits will begin from that completed procedure day.

In the instance that the Day 42 FBF procedure needs to be repeated, participants should either continue receiving the daprodustat dispensed on Day 28, while the participants randomized to darbepoetin alfa should receive an appropriate dose on Day 42. The safety follow up visit will take place 7-14 days after the final procedure.

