¹⁰ The initial dose of study treatment will be **after** the Day 1/Repeat Day 1 FBF & PWV procedures. Participants will receive **EITHER** daprodustat **OR** darbepoetin alfa.

The final dose of daprodustat will be Day 41 (i.e., the day prior to the FBF & PWV procedures), while the final dose of darbepoetin alfa will be Day 28. If repeat procedures are needed the dosing will be extended (See Section 9.6.1.4).

CONFIDENTIAL

205767

¹¹ See Section 7.2 for details on study treatment adjustment

¹² Applies only to participants on anti-coagulant therapy; further details concerning measurement of the international normalised ratio (INR) and subsequent actions can be found in the study reference manual (SRM).

¹³ If test otherwise performed within 3 months prior to first dose of study treatment, testing at screening is not required

¹⁴ The FBF & PWV assessments are to be performed following confirmation of INR < 3.0 for participants on anticoagulant therapy. The Day 42 FBF & PWV assessments can be delayed up to 1 week (i.e., Day 49), while randomization (Day 1) should be delayed until the participant's INR < 3.0 (Section 9.6.1.1).

¹⁵ Only serious adverse events (SAEs) assessed as related to study participation are collected at this visit. See [Appendix 4](#) for additional details.

¹⁶ As described in Section 9.8

¹⁷ Indicates the procedures to be performed on the repeat visits only if the visit is deemed necessary. See Section 9.6.1.4.

¹⁸ Darbepoetin is only to be given on Day 42 if a Repeat Day 42 is needed.

CONFIDENTIAL

205767

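### An Hgb trigger on Day 42 mandates withdrawal when no standard dose is left to spare; the withdrawal follow-up window and the missing entry floor also clash with the stopping rule

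*Protocol*

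**What the plan says.** **Stopping rule.** Protocol 8.1.2 states that Table 2 "summarizes the Hgb values and corresponding action to be taken at each visit". Each row requires permanent discontinuation and study withdrawal once the value is confirmed. Only the rapid-rise row is limited to one visit. Section 8.1 makes the link general: "Participants that discontinue study treatment will be withdrawn from the study". Section 9 allows no waivers.

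**Dosing.** Under the Schedule of Activities (SoA), "The final dose of daprodustat will be Day 41", "while the final dose of darbepoetin alfa will be Day 28". Later doses arise only when the Day 42 FBF is delayed or repeated. Footnote 18, repeated in SAP 10.2.1, says "Darbepoetin is only to be given on Day 42 if a Repeat Day 42 is needed". Protocol 9.6.1.4 covers both delay and repeat: "participants should either continue receiving the daprodustat dispensed on Day 28", with a darbepoetin dose on Day 42 in the other arm. A repeat for quality reasons is known only after the procedure: "If the FBF fails the quality control (QC) criteria following the Day 42 procedure, one additional attempt may be made" (9.6.1.3).

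**Follow-up.** Completers are seen 7-14 days after the last FBF (SoA footnote 3). Withdrawn participants are seen 7-14 days after the last dose (8.2).

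**Entry.** Inclusion 3 requires HemoCue Hgb of 11.0 g/dL or less at screening and Day 1. No criterion sets a lower value.

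**Analysis set.** The primary comparison uses only the Pharmacodynamic Per-Protocol (PDPP) population, which needs Day 1 and Day 42 data and completion of the protocol. No intent-to-treat set is defined (10.2).

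**The concern.** The Day 42 FBF is the primary measurement. A rule meant to stop dosing also acts at that visit, when on the standard timetable there is nothing left to stop. Loss of the measurement would then depend on Hgb response, a consequence of treatment, in a trial with no intent-to-treat set.

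Other Day 42 safety problems are handled differently. High blood pressure (9.4.2), an abnormal ECG (9.4.3) and a raised INR (9.6.1.1) each allow a delay of up to one week, and none requires withdrawal. On INR the rule is direct: "Only participants with INR < 3.0 are to undergo the FBF & PWV assessments".

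Two related rules also fit badly. The withdrawal follow-up window gives one arm a visit due on or before the day of withdrawal. And eligibility admits a value that the stopping rule says must lead to withdrawal.

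**Working it through.** **1. The plan's own figure.** Inputs: coefficient of variation (CV) 0.277, true difference 25%, 25 per arm, alpha 5% (10.1), taken as two-sided.
- Log SD = sqrt(ln(1 + 0.277²)) = 0.272, which matches the SD in 10.3.4.
- Log effect = ln(1.25) = 0.2231.
- A two-sample t calculation (noncentral t, 48 df) gives 81.1%, against 80% in 10.1 and 81% in 10.1.1. The figure reproduces.

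**2. Table 2 rows that act on Day 42**

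| Row | Limited to one visit? | Acts on Day 42? |
|---|---|---|
| Below 7.5 g/dL | No | Yes |
| Fall of 2.0 or more over 2 weeks | No | Yes |
| Rise of 1.3 or more over 2 weeks | Yes (Day 15) | No |
| 13.0 g/dL or above | No | Yes |

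The last standard doses are Day 41 and Day 28, so none remains on Day 42 unless FBF is delayed or repeated. The protocol does not state the order of HemoCue and FBF on Day 42; footnote 4 fixes it only for eligibility checks before FBF. Loss of the FBF is therefore possible, not certain.

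**3. Follow-up after withdrawal on Day 42**
- Darbepoetin: 28 + 7 to 28 + 14 = Day 35-42 (42 + 3 = Day 45 if the SoA window applies).
- Daprodustat: 41 + 7 to 41 + 14 = Day 48-55 (55 + 3 = Day 58 on the same basis).
- Completers: 42 + 7 to 42 + 14 = Day 49-56.

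The window closes 42 - 42 = 0 days after withdrawal for darbepoetin and 55 - 42 = 13 days after it for daprodustat.

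**4. Entry.** Any Hgb below 7.5 g/dL is also at or below 11.0 g/dL. It meets inclusion 3 and a Table 2 withdrawal value at the same visit.

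**5. Power.** Enrolment runs until 50 are in the PDPP, so losses cost recruitment, not power. At assumed losses of 4% and 8%, 50/0.96 = 52.1 and 50/0.92 = 54.3, or 53 and 55 randomized.

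**6. Possible shift in the estimate (illustration only).** The documents give no trigger rate and no correlation between Hgb and FBF response. Assume the top fraction p of Hgb responders is lost from one arm, with correlation rho.
- Shift in the arm mean = rho × SD × φ(z)/(1 - p), where z is the upper p quantile and φ the normal density.
- SE of the log difference = 0.272 × sqrt(2/25) = 0.0769.

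| p | rho | Log shift | Ratio | In SE |
|---|---|---|---|---|
| any | 0 | 0 | 0% | 0 |
| 1/25 | 0.2 | 0.0049 | 0.5% | 0.06 |
| 1/25 | 0.5 | 0.0122 | 1.2% | 0.16 |
| 2/25 | 0.2 | 0.0088 | 0.9% | 0.11 |
| 2/25 | 0.5 | 0.0220 | 2.2% | 0.29 |

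Losses from the lower tail, which two of the three rows would produce, give the same sizes in the opposite direction. Similar losses in both arms would tend to cancel.

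**The case against.** The strongest reply is that other provisions limit each consequence. Most of it stands.

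- **Safety follow-up.** A reader might infer that a darbepoetin participant withdrawn on Day 42 goes unmonitored. The documents do not support that. Clinically significant laboratory values are repeated until they resolve (9.4.4, Appendix 2), and SAEs and adverse events of special interest are followed to resolution or stabilization (9.2.3). Counted from the last dose, the arms get equal windows. What remains is a scheduled visit that cannot work as intended for a Day 42 withdrawal.
- **PDPP status.** A reader might infer that a withdrawn participant drops out of the PDPP even if FBF was done. The SAP leans the other way. Its section 2.1 restricts exclusions to the deviations listed in 10.1.1 so as to keep as many participants as possible, and its 8.1.4 describes the PDPP by having FBF on both days. Protocol 5.3 does not settle the matter, but the clear loss arises only when HemoCue is read first.
- **Order of procedures.** The Study Reference Manual holds the detailed FBF procedure and was not available, so the order may be set there.
- **Entry.** A reader might infer that participants below 7.5 g/dL would be cannulated. Table 2 read strictly also acts on Day 1, where footnote 4 puts HemoCue before FBF. Exclusions 27 (anticipated transfusion) and 32 (investigator judgement) are further guards. None is a numeric entry limit, so the overlap remains.
- **Purpose of the rule on Day 42.** Dosing continues when FBF is delayed or repeated, so an Hgb stop is needed there, and avoiding cannulation at an extreme Hgb is legitimate. Both aims can be met without mandatory withdrawal.

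**Conclusion.** The point holds in a narrow form and is worth considering. Three Table 2 rows mandate withdrawal at the primary-measurement visit when no standard dose remains. The follow-up rule gives a darbepoetin participant withdrawn that day a window of Day 35-42. Entry and stopping limits overlap below 7.5 g/dL. All three follow from the text alone.

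The size is unknown and probably small. The 0-2.2% range (0 to 0.29 SE) rests on an assumed rate, an assumed correlation and loss in one arm only. A first value of 13.0 g/dL or above on Day 42 is probably uncommon at daprodustat doses of 1-4 mg.

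It would be tempting to conclude that the primary comparison is biased or underpowered. The documents give no trigger rate and no direction, and enrolment to 50 evaluable participants protects power. Nor are the reported results materially affected: SAP 2.1 and 10.1.1 record termination, 4 completers, descriptive summaries only and no per-protocol exclusions. The value of the correction lies in the design and in any protocol that reuses it.

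**What to change.** 1. **Protocol 8.1.2, as an exception to 8.1.** A confirmed Table 2 value at the Day 42 visit, or at a delayed or repeat Day 42 visit, bars all further study doses but does not by itself require withdrawal. FBF and pulse wave velocity are done at that same visit unless the investigator judges cannulation unsafe or another rule prevents it, such as INR of 3.0 or above. Only FBF that passes quality control and was obtained at that visit or earlier counts for the PDPP. No later delayed or repeat FBF is done off treatment. This last condition matters because SAP 8.1.2 lets repeat data replace the original.
2. **Protocol 8.2.** For anyone stopped at or after Day 42, follow-up is 7-14 days after that visit in both arms.
3. **Protocol 6.1.** Require HemoCue Hgb of at least 7.5 g/dL at screening and Day 1. The sponsor may set it higher.

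The cost is a short paragraph and two clauses. The downsides are slightly narrower eligibility, a case-by-case cannulation judgement at an extreme Hgb, and no repeat FBF for those few participants.

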7.1.1. Study Treatments

7.1.1.1. Daprodustat Dosing Information

Daprodustat will be administered orally once daily starting **after** the completion of the FBF & PWV procedures on Day 1. The only exception to this is if a Repeat Day 1 is necessary (See Section [9.6.1.4](#)).

Daprodustat Starting Dose

[figure not shown]
All participants randomized to the daprodustat group will be dosed with 2 mg orally once daily starting on Day 1 (See Section 5.5)

Daprodustat Dose Adjustment Algorithm

Participants randomized to daprodustat will have doses adjusted, as required, to target Hgb within the range of 10.0 to 12.0 g/dL. Dose adjustments will be assigned **automatically** via the IWRS (Interactive Web Response System) based on the participant's Hgb value via onsite HemoCue assessment according to the algorithm in Table 1 on Day 28 as noted in the SoA (See Section 2).

The available dose steps for daprodustat are outlined in Figure 2 (highlighted box indicates starting dose). Dose adjustments will result in the daprodustat dose being increased or decreased by **one dose step (up or down) at a time**.

Figure 2 Daprodustat Dose Steps

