7.2. Dose Modification

Doses of daprodustat can be modified on Day 28 based on the participant's Hgb level as measured using the HemoCue device. The dose modifications, based on the Hgb value and change from previous measurement, are found in [Table 1](#).

Doses of darbepoetin alfa can be modified on Day 28 based on the participant's Hgb level as measured using the HemoCue device based on local product labelling, clinical practice guidelines, and clinical judgement.

Table 1 Daprodustat Dose Modification Algorithm

Hgb (g/dL)	Hgb change since Day 1 visit	Dose Adjustment
< 7.5	Any change	Repeat HemoCue assessment on the same sample at same study visit to confirm; take average of 2 values. If confirmed, permanently discontinue study treatment and withdraw subject from the study (See Section 8.1.2).
≥7.5 to < 10.0	Decreasing or No change (i.e., < 0.5 g/dL increase)	Increase to the next higher dose step
≥7.5 to < 10.0	Increasing by at least 0.5 g/dL	Maintain dose
≥10.0 to ≤ 12.5	Any change	Maintain dose
> 12.5 to < 13.0	Increasing or No change	Decrease to the next lower dose step
	Decreasing	Maintain dose

Hgb (g/dL)	Hgb change since Day 1 visit	Dose Adjustment
≥13.0	Any change	Repeat HemoCue assessment on the same sample at same study visit to confirm; take average of 2 values. If confirmed, permanently discontinue study treatment and withdraw subject from the study (See Section 8.1.2).
≥7.5 - <13.0	≥1.3 g/dL increase in Hgb over the previous 2 weeks (as assessed on Day 28 only) ¹	Repeat HemoCue assessment on the same sample at same study visit to confirm; take average of 2 values. If confirmed, decrease to next lower dose step (see Section 7.1.1)
≥7.5 - <13.0	>2 g/dL increase in Hgb over the previous 4 weeks.	Repeat HemoCue assessment on the same sample at same study visit to confirm; take average of 2 values. If confirmed, decrease to next lower dose step (see Section 7.1.1)

¹ If increase in Hgb >1.3 g/dL is noted on Day 15, please refer to Hgb Stopping Criteria Table below (Section 8.1.2).

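### At Day 28 the daprodustat dose table (Protocol 7.2, Table 1) and the Hgb stopping table (8.1.2, Table 2) give inconsistent actions for a confirmed two-week Hgb fall of 2.0 g/dL or more

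*Protocol*

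**What the plan says.** **Stopping rule.** Section 8.1.2 says that Table 2 "summarizes the Hgb values and corresponding action to be taken at each visit". One row covers Hgb from 7.5 to below 13.0 g/dL with a "≥2.0 g/dL decrease in Hgb over the previous 2 weeks". The HemoCue reading is repeated and the two values averaged, and then: "If confirmed, permanently discontinue study treatment and withdraw participant from the study". The fall row has no day limit. The rapid-rise row does: it is confined to the first two-week visit, and a footnote sends a Day 28 rise to Section 7.2. Section 8.1 makes the criteria binding: "A participant must discontinue study treatment for the pre-specified reasons below", with the Hgb criteria first on its list.

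**Dose rule.** Section 7.1.1.1 has the IWRS assign daprodustat dose changes automatically, "based on the participant's Hgb value via onsite HemoCue assessment according to the algorithm in Table 1 on Day 28". Apart from its rapid-rise rows, Table 1 in Section 7.2 works from current Hgb and the change since Day 1:

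- Hgb 7.5 to below 10.0, "Decreasing or No change (i.e., < 0.5 g/dL increase": "Increase to the next higher dose step". The size of the decrease is not limited.
- Hgb "≥10.0 to ≤ 12.5": dose unchanged, whatever the change since Day 1.
- Hgb below 7.5, or 13.0 and above: the stop is written out, with a reference to Section 8.1.2.
- Rapid rise over two or four weeks: one step down if confirmed.

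Table 1 has no row, footnote or cross-reference for a rapid fall. It applies to daprodustat only; darbepoetin changes follow local labelling, guidelines and clinical judgement.

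**The concern.** Day 28 is the only scheduled dose-adjustment visit. One HemoCue reading there can satisfy a Table 2 stopping row and, at the same time, a Table 1 row that raises or keeps the dose. The protocol itself treats a fall of this size as serious enough to end treatment. Staff who work from the dosing table alone would not see that rule, and they would see two other stops written out in full. At stake is whether that participant leaves the study or stays on daprodustat, possibly at a higher dose: the starting dose is 2 mg and the listed levels are 1, 2 and 4 mg.

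**Working it through.** The plan gives no figure to reproduce here. The check is whether an eligible participant can meet both tables at once, and what Table 1 then says.

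**Inputs.** H1, H14 and H28 are Hgb in g/dL at Days 1, 14 and 28.

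- Entry (Section 6.1): H1 ≤ 11.0.
- Not stopped at Day 14 (Table 2): H14 from 7.5 to below 13.0, H1 − H14 < 2.0, and H14 − H1 < 1.3, which is at most 1.2 in steps of 0.1.
- Table 2 fall row at Day 28: 7.5 ≤ H28 < 13.0 and H14 − H28 ≥ 2.0.
- Table 1, step up: 7.5 ≤ H28 < 10.0 and H28 − H1 < 0.5.
- Table 1, unchanged: 10.0 ≤ H28 ≤ 12.5, any H28 − H1.

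**Two examples**, taking the Day 28 value as the confirmed average:

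| H1, H14, H28 | H14 − H1 | H14 − H28 | H28 − H1 | Table 1 | Table 2 |
|---|---|---|---|---|---|
| 9.8, 10.6, 8.5 | 0.8 | 2.1 | −1.3 | one step up | stop and withdraw |
| 11.0, 12.2, 10.1 | 1.2 | 2.1 | −0.9 | unchanged | stop and withdraw |

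Both meet the entry limit and neither is stopped at Day 14.

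**General case.** If the rise rule works at Day 14, then H28 ≤ H14 − 2.0 ≤ (H1 + 1.2) − 2.0 = H1 − 0.8. Every rapid fall at Day 28 is therefore also a decrease since Day 1, and the rapid-rise rows of Table 1 cannot apply. Because H1 ≤ 11.0, H28 is at most 10.2. Two branches remain:

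- **Step up:** H28 from 7.5 to 9.9.
- **Unchanged:** H28 from 10.0 to 10.2. This needs H14 from 12.0 to 12.2 and H1 from 10.8 to 11.0.

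Enumerating all paths in 0.1 g/dL steps, with H1 from 7.5 to 11.0, gives 4,050 paths with a step up, 10 unchanged, and none with a stop or a decrease. These count grid points; they are not probabilities. The step-up branch is the main one.

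**Sensitivity to a day label.** Table 2 ties the rise rule to Day 15, but the schedule has a Day 14 visit and no Day 15 visit. If the rule is not applied at Day 14, H14 can reach 12.9 and H28 can reach 10.9. The counts become 17,060 step up, 3,520 unchanged through the row for a rise of at least 0.5 g/dL (H28 from 8.0 to 9.9), and 1,540 unchanged through the 10.0 to 12.5 row (H28 from 10.0 to 10.9). A further 440 + 120 = 560 unchanged paths also meet the four-week rise row, which calls for a step down. Again, Table 1 never gives a stop.

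**The case against.** The strongest reply is that the protocol already settles precedence. Section 8.1 is mandatory, and a participant who has stopped for good has no dose to modify. Where the authors wanted a Day 28 reading handled by Section 7.2 and not by Table 2, they said so for the rapid rise; they did not for the fall. The excessive-erythropoiesis row of Appendix 7 cites Sections 7.2 and 8.1 together, including for rate of change. The two end rows of Table 1 may be there only to close the Hgb scale, and nothing calls the table exhaustive.

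Much of this stands. A reader might infer two instructions of equal force; the documents do not support that, because the wording of Section 8.1 favours Table 2. The inconsistency remains all the same:

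- The end rows of Table 1 do more than close a scale. They state the stop and refer to Section 8.1.2.
- The footnotes in both tables reconcile the rapid rise and nothing else.
- Section 7.1.1.2 sends darbepoetin users to Section 8.1.2 for stopping criteria; Section 7.1.1.1 has no such pointer for daprodustat.
- The drug-interaction row of Appendix 7 names Section 7.2 alone for Hgb-based adjustment, interruption or discontinuation, and this stop is missing there.

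A reader might also infer that the IWRS would in fact escalate the dose. The documents show only that it assigns adjustments from Table 1. Its specification and the SRM are not among them, so whether it also checks the stopping criteria is unknown.

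**Conclusion.** The inconsistency is real and eligible participants can reach it. For a confirmed two-week fall of at least 2.0 g/dL at Day 28, with Hgb from 7.5 to below 13.0, Table 2 requires permanent discontinuation and withdrawal. Table 1 gives a dose increase over most of the overlap and no change in a narrow part of it. It concerns the daprodustat arm only, depends on the repeat reading confirming the value, and has its narrow second branch only if the rise rule operates at Day 14.

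The situation is expected to be rare. The documents give no Hgb variability, so no rate is stated.

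A reader might infer that the choice of table would shift the primary comparison through membership of the PDPP population. The documents do not support that. Continuing a participant who met a mandatory stop would be a departure from the protocol, not a second route into that population. SAP Section 2.1 also reports that the study was terminated with 4 completed subjects and that only summary statistics will be produced. No effect on PDPP inference is claimed.

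Severity: a moderate internal-consistency and safety correction.

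**What to change.** Reconcile Table 1 and Table 2 for a confirmed fall of 2.0 g/dL or more over the previous two weeks at Day 28. Then carry the agreed action, or an explicit statement of which table takes precedence, into Table 1 and the IWRS, as Table 1 already does for values below 7.5 and at 13.0 or above. Which action is right is for the sponsor's clinical team.

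The cost is one table row or cross-reference and one IWRS check. No new data are needed, because the existing two-week rise row already uses the Day 14 value.
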